To investigate feasibility of an 8-week progressive home-based exercise intervention and change in patient-reported symptoms and pelvic tilt, in a prospective cohort of patients with radiographic verified acetabular retroversion, and excessive anterior pelvic tilt.

Primary hypothesis:

In a paired design, the improvement in '*The Copenhagen Hip and Groin Outcome Score*' pain-subscale (HAGOS questionnaire), following an 8-week exercise intervention, will be larger in comparison with the prior control period.

Secondary hypotheses:

- The exercise intervention is feasible in terms of adherence to exercise, exercise-related pain, drop-outs, and adverse events.
- The improvements in the remaining HAGOS subscale scores on symptoms, level of function, and quality of life, following an 8-week exercise intervention, will be larger in comparison with the control period.
- The improvements in the EQ-5D-3L questionnaire, following an 8-week exercise intervention, will be larger in comparison with the control period.
- The reduction in the degree of anterior pelvic tilt evaluated by EOS imaging, following an 8-week exercise intervention, will be larger in comparison with a control period.

STUDY METHODS

Design

The study was designed as a single-center, non-consecutive, unblinded prospective cohort study using patients as their own controls. The change between an 8-week control period prior to the intervention and the following 8-week exercise period will be reported.

Exercise intervention

A physiotherapist (the project manager) informed the patients about the relation between the hip condition and the purpose of the exercise program, provided advice on activity and sports modification, and instructed in exercises. The exercise program was an 8-week progressive home-based exercise intervention with optional, supervised booster-sessions and opportunity to contact the project manager by mail or phone in case of questions regarding the exercise program. After the 8-week exercise period was completed, the patients were encouraged to continue with the exercise program for another 16 weeks.

The exercise program was standardized and non-supervised consisting of four general elements: stretching for posterior pelvic tilt mobility, strengthening hip abductors and extensors, improving body core stability, and movement control for actively tilting and/or keeping the pelvis posteriorly.

Statistical Analysis plan

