Time points at which the outcomes were measured are presented in Table 1. Outcomes are defined in the *Analysis* section.

Table 1 – Timing of outcome assessments

Outcomes	Control period	Baseline	Primary endpoint
		Minus 8-weeks before exercise intervention	Start-up of exercise intervention
Primary outcome			
PROM: HAGOS pain subscale	x	x	x
Secondary outcomes			
PROM: HAGOS remaining five subscales	x	x	x
EQ-5D-3L	x	x	x
EOS scanning: Pelvic tilt	x	x	x
Explorative outcomes			
PROM: Global Perceived Effect			x
Oxford Hip Score	x	x	x

Abbreviation: PROM (Patient-Reported Outcome Measure)

STATISTICAL PRINCIPLES

Descriptive data and fitted regression residuals from the mixed-effects linear regression model will be visually assessed for Gaussian distribution by use of QQ-plots and frequency histograms, and statistically tested using the Shapiro-Wilk test. Parametric and/or non-parametric statistical analyses will be used appropriately. A two-tailed P-value of $P \leq 0.05$ will be considered statistically significant, and estimates will be presented with 95% confidence intervals. A primary analysis following the Intention-To-Treat (ITT) principle and a secondary Per Protocol (PP) sensitivity analysis will be conducted (elaborated later in the *Analysis* section).

Adherence

Adherence to the exercise program (frequency) was recorded in a self-reported training diary. Adherence was defined as at least 75% completion of the prescribed exercise program in the 8-week period. The patients were instructed to exercise 3-4 times a week (i.e. 24-32 times over eight weeks) accordingly. Thus, at least 18 exercise sessions (75% of 24 exercise sessions), must have been completed to achieve acceptable compliance.

Exercise-related pain and adverse events

Exercise-related pain was recorded in a self-reported training diary, from 0-10 on a Numeric Ranking Scale (NRS) before, during and after exercising. A level of hip-related pain equal to and above 5 was defined as alarming values and subsequently adjustments were done as described above. Potential adverse events were noted in the training diary or reported by phone and email to the project manager. The use of hip-related analgesics and general comments on the exercise program were noted in the diary.

Protocol deviations

The following minor adjustments/additions were made after trial registration on Clinicaltrials.gov and inclusion of the first patient.

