- The assessment of feasibility was added to the study objective because of the novelty and potential importance of the exercise program.
- The secondary outcome '*Radiographic measurement of pelvic tilt in the frontal plane, defined as the distance (in mm.) between the sacro-coccygeal joint and the symphysis*' was changed to the '*Radiographic measurement of pelvic tilt in the sagittal plane, defined as the angle (in degrees) between a horizontal line and a line connecting the upper border of the symphysis with the sacral promontory*'. From inspecting our radiographic data, we learned that pelvic tilt measured in the sagittal plane were more reliable compared to frontal plane images. Moreover, the adjustment resulted in that no images had to be excluded due to poor image quality.
- Due to two dropouts early in the study, two additional patients were recruited. However, since only one patient subsequently dropped out, a total of 39 patients completed the training out of 42 included patients.
- Three patients did not get the last EOS-scanning done after the end of the exercise period due to pregnancy (n=2) and a defect apparatus (n=1).

TRIAL POPULATION

Patients between 18 to 40 years old were included from Odense University Hospital outpatient clinic (Denmark), with verified acetabular retroversion (positive COS and PWS) from a frontal pelvic radiograph in standard standing position, not eligible for periacetabular osteotomy and able to take part in the intervention. Patients were excluded if they had a pelvic-tilt-ratio greater than 0.5 (31) (the height of the obturator foramen divided by the height of the lesser pelvis) indicating posterior pelvic tilt, radiographic sign of hip osteoarthritis (< 2 mm. joint space), previous lumbar, pelvic or hip related surgery, conditions not allowing exercise therapy, a body mass index (BMI) above 35 and not understanding spoken and/or written Danish language.

Flowchart of patients' progress through the study is presented in Figure 1.

Statistical Analysis plan

[figure not shown]

Figure 1 – Flowchart of patients' progress through the study

Patient characteristics are presented in Table 2.

Table 2 – Patient characteristics at the beginning of the control period (n=42)

Patient characteristics	
Sex, male/female, n (%)	
Age, years	
BMI, kg/m ²	
Height, m	
Weight, kg	
Affected hip	
Bilateral, n (%)	
Left, n (%)	
Right, n (%)	
Patient-reported outcome measures	
HAGOS, score from 0 to 100	
Pain	
Symptoms	

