3. Between-period change in pelvic tilt (in degrees) was measured with EOS scanning in standing position in the sagittal plane as the angle between a horizontal line and a line connecting the upper border of the symphysis with the sacral promontory (34). EOS® imaging system is a low-radiation roentgen scanner capturing the selected body part of a person in a standardized standing position with the option to acquire orthogonal views simultaneously in the frontal- and sagittal plane (35). EOS provides diagnostic qualities similar to conventional X-ray using 44 % less radiation when radiographic signs of acetabular retroversion are assessed (36). EOS® imaging system has shown excellent reliability in measuring the sagittal alignment of the pelvis (37). In comparison with radiographs, EOS® is found valid (38) and reliable (39) in assessing pelvic configurations.

Data quality

All patient-reported outcomes will be entered twice to check for entry errors. Fifty randomly selected sagittal EOS scans across the three time points will be assessed for inter-observer reliability regarding pelvic tilt.

Analysis methods

Repeated measurements from a particular patient are likely to be more similar to each other than measurements from different patients, and this correlation needs to be considered in the analysis of the resulting data (40). Longitudinal measurements are not independent of one another, due to the individual baseline value, and time factor, which must be taken into account (40).

A mixed-effects linear regression model will be used accordingly to the longitudinal design and will accommodate missing data in the analysis under the assumption “missing at random,” thus, the analyses will follow the *Intention To Treat* (ITT) principle (40).

Primary analysis:

Under the assumption of normal distributed residuals, a mixed-effects linear regression model will be used to investigate the between-period change on the dependent continuous outcome variable (HAGOS subscale pain). A dummy-coded variable, indicating the three time points at which the measurement was taken, is framing the control period and the intervention period.

Sensitivity analysis:

A ‘*Per-Protocol analysis*’ for patients demonstrating the a-priori-defined acceptable adherence to exercise ($\geq 75\%$) will be performed.

Secondary analysis:

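### The SAP declares the study unblinded and states no masking of pelvic tilt readers to time point, and its only reader check cannot detect a shift that the readers share.

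*SAP*

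**What the plan says.** The Design section describes a "single-center, non-consecutive, unblinded prospective cohort study using patients as their own controls". It makes no exception for outcome assessment.

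Item 3 of the secondary outcome definitions reads: "Between-period change in pelvic tilt (in degrees) was measured with EOS scanning in standing position in the sagittal plane". The measure is "the angle between a horizontal line and a line connecting the upper border of the symphysis with the sacral promontory", so each reading needs the symphysis and the promontory to be located on the image. Table 1 schedules the scan at three time points: eight weeks before exercise, at its start and at its end. No other imaging outcome appears there.

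The secondary hypotheses state the expected direction: "The reduction in the degree of anterior pelvic tilt evaluated by EOS imaging, following an 8-week exercise intervention, will be larger" than over the control period.

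On the quality of the readings, the Data quality section says only this: "Fifty randomly selected sagittal EOS scans across the three time points will be assessed for inter-observer reliability regarding pelvic tilt". The SAP does not name the readers or the software, and it says nothing about masking or reading order, either for the main readings or for the 50-scan sample.

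**The concern.** Patients cannot be blinded to an exercise programme, but a stored image can be read without its date. In this design the order is fixed, with control period first and exercise second, so a reader who knows the visit also knows the condition. The hypothesis tells that reader which way the angle should move.

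The planned safeguard does not address this. Inter-observer agreement measures how far readers scatter around each other. If both know which scan is post-exercise and both place the landmarks slightly towards less anterior tilt, they still agree and the shift stays in the data.

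At stake is the only Table 1 outcome that is not a patient questionnaire, and the one that tests whether the programme changes pelvic tilt at all.

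**Working it through.** **Inputs.**
- Three scans per patient (Table 1): Y1 at minus 8 weeks, Y2 at the start of exercise, Y3 at the end of exercise.
- "a total of 39 patients completed the training out of 42 included patients" (Protocol deviations). The same section reports three missed last scans.
- Two-sided 5% significance level (Statistical principles).
- The SAP gives no SD, measurement error or target difference for tilt, so it has no tilt figure to reproduce. Its only sample-size figure, 36, concerns HAGOS pain. With a difference of 10 and an SD of 20.6, the exact paired t-test gives 79.7% power at 35 patients and 80.8% at 36, so that figure reproduces. The same calculation is used for the illustration below.

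**Step 1: how a reading shift enters the result.** The between-period change is

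(Y3 − Y2) − (Y2 − Y1) = Y3 − 2·Y2 + Y1.

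- The same shift d on all three scans: d − 2d + d = 0. A reader who is constantly off does no harm.
- A shift d on the post-exercise scan only: the contrast moves by d.
- A shift d on both pre-exercise scans: d − 2d = −d, which has the same size.

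Only a shift that depends on time point biases the contrast. Masking to time point removes the knowledge that could produce it.

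**Step 2: what a shift would do to the test.** Assume no true change, 36 patients with all three scans (39 − 3, if the three missed scans belong to completers), a paired t-test on the contrast as a stand-in for the mixed model, and a shift at the last scan expressed in SDs of the contrast. The noncentrality is shift × √36 = 6 × shift. The rejection rates at a nominal 5% are:

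| Assumed shift (SD of contrast) | Noncentrality | 36 patients | 39 patients |
|---|---|---|---|
| 0.1 | 0.6 | 9% | 9% |
| 0.2 | 1.2 | 21.5% | 23% |
| 0.3 | 1.8 | 42% | 45% |
| 0.5 | 3.0 | 83% | 86% |

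These shifts are assumptions. They cannot be converted to degrees, because no SD for tilt is given.

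**Step 3: how many images are involved.** Three scans for 42 patients make 126. Less the three missed scans, and less one last scan for each of three dropouts, this leaves 126 − 3 − 3 = 120. If the dropouts contributed no scans, it is 39 × 3 − 3 = 114. The 50-scan check covers 50/126 = 40% to 50/114 = 44% of them. That is ample for inter-observer agreement, but no sample size would make agreement sensitive to a shared shift.

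**The case against.** The strongest reply is that this rests on silence. How images are read is often set out in a protocol or imaging procedure, and neither is at hand. The word unblinded may refer only to patients and therapist. Nothing in the SAP says that a reader knew the visit. This stands to the extent that the point must be worded as no masking stated, not as unmasked reading shown. It does not dispose of the point. The SAP takes up reader quality itself, sets its own check, and labels the whole study unblinded, so someone following it as written has no reason to mask.

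Several stronger readings are tempting but not supported:
- **That the readings are already contaminated.** Protocol deviations says "From inspecting our radiographic data, we learned that pelvic tilt measured in the sagittal plane were more reliable", so images were looked at before the measure was changed. But the reasons given are reliability and image quality. The SAP does not link that inspection to treatment effect, or say that the same people read the outcome.
- **That the landmarks are placed by hand.** The definition and the planned observer comparison suggest human reading, but the SAP does not say so.
- **That tilt is the study's only outcome not rated by patients.** It is not. A subsample has strength and motion-laboratory outcomes, and drop-outs are counted as a feasibility outcome.
- **That the bias could be doubled.** A shift on the start-of-exercise scan alone would move the contrast by 2d, but both earlier scans precede exercise. An expectation about pre-exercise scans would affect them alike and give a net shift of size d.
- **That the reliability sample is wrongly drawn.** Fifty random scans suit the stated aim of inter-observer reliability. Sampling about 17 patients with all three scans would say more about error in change but would cover fewer patients. That is an optional trade-off and not part of this point.

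It is also fair to say that masking readers protects only the reading. Patients are trained to tilt the pelvis posteriorly while standing and are then scanned standing. A posture adopted for the scan would pass through masked reading unchanged.

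**Conclusion.** The point holds as a gap in the safeguards for one secondary outcome. The SAP declares the study unblinded, states no masking of tilt readers to time point, and relies on an agreement check that cannot reveal a shift common to the readers. A time-dependent shift of d degrees on the post-exercise scan biases the between-period contrast by d.

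Whether such a shift exists, and how large it might be, cannot be told from the SAP. The error rates in the working show sensitivity under assumed shifts and are not estimates. HAGOS pain, the primary outcome, is not affected. The change is worth making because the risk is avoidable at little cost, but the plan's main conclusion does not depend on it.

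**What to change.** Add to Data quality, with a cross-reference from item 3 of the secondary outcome definitions, that all sagittal EOS scans, including the 50 in the reliability sample, are de-identified, stripped of date and visit, put in random order across patients and visits, and read by the existing readers masked to time point. If scans have already been read unmasked, they are re-read in this way. State that the masked readings are the ones analysed.

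If masked reading has already been done, one sentence saying so is enough. If it cannot be done, the SAP should state that reading was unmasked and the report should list this as a limitation.

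The cost is anonymising about 120 stored images and, at most, one further reading by the same staff. No patient procedure and no additional reader is needed. The report should still note that masked reading does not guard against patients altering their stance during the scan.

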Each exercise session began with stretching exercises, followed by muscle strength training and ended with specific posture improving exercises on tilting the pelvis posteriorly.

The exercise program was intended to be completed three to four times a week, with a rest day in between. In the first two weeks (module I), the duration of the exercise program was approximately 30 minutes to complete. For the remaining six weeks (module II), the exercise program gradually took longer time to complete (i.e. 45 min.), as the number of repetitions increased.

In case of any adverse events, or other challenges related to the exercise program, the project manager was contacted, and a booster-session was arranged. In cases of drop-outs, the referring physician decided whether the patient should be seen in the outpatient clinic again.

Experienced hip-related pain exceeding 4 on a 0-10 scale, where 0 = *no pain* and 10 = *worst possible pain*, was considered as alarming pain and the exercises was subsequently adjusted. The level of pain before, during, and after exercise were noted in the training diary along with the use of over-the-counter analgesics.

Overview of the progression of exercises

Module I – Exercises (first two weeks)	Week 1-2
#1 Stretching the anterior hip	2 sets of 30 sec.
#2 Stretching the low back	2 sets of 30 sec.
#3 Stretching the anterior thigh	2 sets of 30 sec.
#4 Strengthening the hip abductors	2 sets of 10 reps.
#5 Strengthening the hip external rotators (Clamshell)	2 sets of 10 reps.
#6 Spinal mobility (Cat & Camel)	1 set of 10 reps.
#7 Core stability (Bird Dog)	3 sets of 10 reps.
#8 Movement control in lying (Pelvic tilt)	2 sets of 10 reps.
#9 Core stability (Static plank)	2 sets of 15 sec.
#10 Strengthening the abdominal muscles (Crunch)	2 sets of 10 reps.
#11 Strengthening the abdominal muscles (Oblique crunch)	2 sets of 10 reps.
#12 Movement control in standing (Supported pelvic tilt)	1 set of 10 reps.
#13 Movement control in standing (Unsupported pelvic tilt)	1 set of 10 reps.

Module II – Exercises (from week 3 to 8)	Week 3-4	Week 5-6	Week 7-8
#1 Stretching the anterior hip	2 sets of 30 sec.	2 sets of 30 sec.	2 sets of 30 sec.
#2 Stretching the low back	2 sets of 30 sec.	2 sets of 30 sec.	2 sets of 30 sec.
#3 Stretching the anterior thigh	2 sets of 30 sec.	2 sets of 30 sec.	2 sets of 30 sec.
#4 Strengthening the hip abductors	2 sets of 10 reps.	3 sets of 10 reps.	4 sets of 10 reps.

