#5 Strengthening the hip external rotators (Clamshell)	2 sets of 10 reps.	3 sets of 10 reps.	4 sets of 10 reps.
#6 Spinal mobility (Cat & Camel)	1 set of 10 reps.	1 set of 10 reps.	1 set of 10 reps.
#7 Movement control in lying (Dying bug)	2 sets of 10 reps.	3 sets of 10 reps.	4 sets of 10 reps.
#8 Movement control in lying (Single leg pelvic tilt)	2 sets of 10 reps.	3 sets of 10 reps.	4 sets of 10 reps.
#9 Strengthening the hip extensors	2 sets of 10 reps.	3 sets of 10 reps.	4 sets of 10 reps.
#10 Core stability (Dynamic plank)	2 sets of 10 reps.	3 sets of 10 reps.	4 sets of 10 reps.
#11 Movement control in standing (Sup. pelvic tilt)	1 set of 10 reps.	1 set of 10 reps.	1 set of 10 reps.
#12 Movement control in standing (Unsup. pelvic tilt)	1 set of 10 reps.	1 set of 10 reps.	1 set of 10 reps.

Abbreviations: Sec.=Seconds, Reps. Repetitions, Sup.=Supported, Unsup.=Unsupported

Selection of subsample for physical performance assessment

A subsample (20 patients) of the included patients was randomly selected to be investigated for isometric muscle strength, kinematic and kinetic outcomes during gait and functional tasks in a 3-dimensional motion laboratory. The explorative outcomes will be reported in secondary analyses not specified in the current SAP.

Sample size

The sample size calculation was based upon paired means calculation. The minimal clinical important difference (MCID) for the HAGOS pain-subscale was estimated being 10 % (half a standard deviation) (30). A minimum of 36 patients was required (10 % pre-posttest difference on HAGOS pain-subscale, SD=20.6 (30), alpha = 0.05, power = 80 %). An additional of four patients were added due to the risk of dropout.

Stopping guidance

There was no overall stopping guidance in the study or interim analysis of adverse effects. However, the training was stopped, and the referring physician contacted if individual patients experienced pain above 4 on a 0-10 Numeric Ranking Scale related to the training program, that could not be reduced by adjusting the exercises during a booster-session.

Timing of analysis

The primary endpoint was after the 8-week exercise period.

There were four time points at which the outcomes were measured, framing three consecutive periods: control period, exercise period, and an additional 16-weeks exercise period. Analysis of data from the 16 weeks of additional exercise is not a part of this SAP.

Timing of outcome assessments

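### Does the plan need a further sensitivity analysis because the per-protocol analysis cannot probe the missing-at-random assumption?

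*SAP*

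**What the plan says.** Under Analysis methods, the SAP says that the mixed-effects model "will accommodate missing data in the analysis under the assumption" of missing at random, and on that basis describes the analysis as intention to treat (ITT). The Statistical principles section names two analyses: "A primary analysis following the Intention-To-Treat (ITT) principle and a secondary Per Protocol (PP) sensitivity analysis will be conducted". The Sensitivity analysis paragraph has one entry, PP "for patients demonstrating the a-priori-defined acceptable adherence to exercise". The Adherence section turns this into a count: "at least 18 exercise sessions (75% of 24 exercise sessions), must have been completed to achieve acceptable compliance". Table 3 has ITT and PP rows for every outcome and no others.

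On attrition, Protocol deviations reports that "a total of 39 patients completed the training out of 42 included patients". It places two of the three drop-outs early in the study. On follow-up after drop-out, the Exercise intervention section says only: "In cases of drop-outs, the referring physician decided whether the patient should be seen in the outpatient clinic again". Stopping guidance says that "the training was stopped, and the referring physician contacted if individual patients experienced pain above 4 on a 0-10 Numeric Ranking Scale", where adjusting the exercises had not helped. The readable text does not say why the three left, or which HAGOS scores they have. The patient-flow figure, which might, is not reproduced in the text at hand.

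**The concern.** A sensitivity analysis usually varies an assumption on which the primary analysis depends. Here the assumption is missing at random, and PP leaves it untouched. PP also selects on something that happens after the start of exercise. Eighteen sessions at three to four a week take 4.5 to 6 weeks, so a patient whose training is stopped early for pain cannot qualify, and pain is what the primary outcome measures.

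Two things seem to be at stake. A reader of Table 3 could take close ITT and PP estimates as evidence that the result is robust to drop-out, when the exercise-period change of the drop-outs may be observed in neither row. And if patients who stopped fared worse than the model predicts, the between-period improvement in HAGOS pain would be overstated, with nothing in the plan to show by how much.

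**Working it through.** **Figures the plan gives.** Adherence threshold: 0.75 × 24 = 18 sessions; 18/4 = 4.5 weeks and 18/3 = 6 weeks. Non-completers: 42 − 39 = 3, and 3/42 = 7.1%. Sample size: a paired t-test with difference 10, SD 20.6, two-sided alpha 0.05 and 80% power needs 36 patients (power 80.8%), as stated. With 39 patients the same calculation gives 84.0%, so the drop-out does not threaten the planned power.

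**Assumptions.** SD 20.6 at each time point and correlation 0.5 between any two, so that a one-period change also has SD 20.6. With scores Y1 (start of control period), Y2 (start of exercise) and Y3 (primary endpoint), the between-period change is (Y3 − Y2) − (Y2 − Y1) = Y3 − 2·Y2 + Y1. Its SD is √3 × 20.6 = 35.7 and its standard error is 35.7/√42 = 5.5. The smallest estimate significant at 0.05 (t, 41 df) is 11.12.

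**Case A: three patients lack only Y3 and are d points worse than predicted.** The all-patient value lies 3·d/42 below the ITT estimate. The last column is the ITT P-value at which the shifted estimate would sit exactly on the 0.05 boundary.

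| d | Shift (points) | Shift / SE | ITT P at the boundary |
|---|---|---|---|
| 10 | 0.71 | 0.13 | 0.038 |
| 20 | 1.43 | 0.26 | 0.028 |
| 30 | 2.14 | 0.39 | 0.021 |

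The verdict changes only if the ITT P-value falls between the last column and 0.05. If all 42 have scores, the shift is zero.

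**Case B: the two early drop-outs lack both Y2 and Y3 and are d points worse at each.** Each such patient's contrast moves by −d − 2(−d) = +d. For d = 20 the all-patient value is 2 × 20/42 = 0.95 points *above* ITT; simulation gave about 11.2 against 10.3. The bias now runs against the intervention. Lowering only missing endpoint scores would not correct it and could adjust in the wrong direction.

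**Do ITT and PP agree whatever happened to the drop-outs?** Not in general. ITT keeps their earlier scores; PP removes those patients altogether. Let the three patients with the lowest Y2 lose Y3, with a true contrast of 10.

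- Given Y2, the expected contrast is 10 + (0.5 − 2 + 0.5)(Y2 − mean) = 10 − (Y2 − mean).
- The three lowest of 42 average 1.83 SD below the mean, so the other 39 average 3 × 1.83/39 = 0.141 SD above it, or 0.141 × 20.6 = 2.9 points.
- PP therefore averages about 10 − 2.9 = 7.1, while ITT stays at about 10. Simulation gave 7.2 and 10.1.

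If drop-out is unrelated to the observed scores, the average gap between ITT and PP is near zero, but within one trial it is still about 1 point in absolute size. PP also excludes anyone below 18 sessions who did stay in the study, a number the plan does not give.

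**The case for a change.** The best case for a change is this. Missing-data assumptions and sensitivity analyses belong in a SAP, and this one states both. It attaches the sensitivity label to an analysis that cannot bear on the assumption behind the primary result. If non-completers have no endpoint score, PP drops them; if they have one, PP discards observed data and differs from ITT through selection. Either way the assumption goes unexamined. A delta-adjusted row for HAGOS pain would need no new data and would leave the primary model and the 18-session threshold alone.

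The reading of the SAP behind this is right, and so is the conclusion that PP says nothing about missing at random. Three things weaken the step to a required change. First, the SAP gives missing data to the mixed model and gives PP the question of effect in adherent patients; adherence is part of its own feasibility hypothesis, so PP has a legitimate job and nothing is misstated. Second, no analysis of observed data can test missing at random. A delta analysis only shows what follows from a chosen departure, and both its size and, as Case B shows, its direction depend on which scores are missing. Third, no readable passage says that any drop-out was pain-related or lacks a HAGOS score.

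**Conclusion.** No change to the plan is called for. The gap is real but minor: one sensitivity analysis is planned, it concerns adherent patients, and the missing-at-random assumption is not varied. No stated rule gives a wrong result, and the ITT estimate is not shown to be wrong.

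Drop-out accounts for at most 3 of 42 endpoint scores. Under the variance assumptions above, the shift is 0.13 to 0.39 standard errors if only endpoint scores are missing and d is 10 to 30; the top of that range is three times the plan's 10-point minimal important difference. The shift is of opposite sign if the early drop-outs lack both later scores and were equally worse at each, and zero if all 42 have scores. It could alter the verdict only for a result already close to 0.05.

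An analyst following this SAP can reasonably report how many of the 42 lack each HAGOS pain score and at which time point. If any are missing, a delta analysis shifting every missing score in both directions is an optional extra. The ITT and PP rows of Table 3 should not be read as evidence on the missing-data assumption, whether they agree or differ.
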